5.4. Investigational Product Supplies

5.4.1. Dosage Form(s) and Packaging

During the double-blind treatment period, blinded tofacitinib and matched placebo will be provided as tablets for oral administration. The tofacitinib 5 mg tablets or placebo tablets will be supplied in bottles and labeled according to local regulatory requirements. The investigational product will be labeled in such a manner that the subject and study staff will be unable to determine from the dispensed packaging to which treatment sequence the subject is assigned. All blinded investigational product will be collected at the Week 16 visit and subjects will receive new investigational product as part of the open-label portion of the study at the Week 16 visit and will receive the first dose of open-label investigational product in the clinic. At the Week 16 visit, all subjects will receive tofacitinib 5 mg tablets supplied in containers and labeled according to local regulatory requirements. Supplies will be labeled as appropriate for this two-arm placebo-controlled, double-blind trial and the open-label treatment period.

5.4.2. Preparation and Dispensing

The investigational product will be dispensed using an IRT drug management system at each visit from Baseline to Week 40 (excluding Week 2). A qualified staff member will dispense the investigational product via unique container numbers in the bottles provided, in quantities appropriate for the study visit schedule. The subject/caregiver should be instructed to

maintain the product in the bottle provided throughout the course of dosing and return the bottle to the site at the next study visit.

The investigational product will be packaged and labeled in such a manner that the subject and study staff will be unable to determine from the dispensed packaging to which treatment arm the subject is assigned during the double-blind treatment period. At study visits sufficient investigational product will be dispensed to complete dosing until the next scheduled visit. The amount of investigational product dispensed at each visit must be recorded. At study visits the subject must return all investigational product and the amount of investigational product returned will be recorded to account for all dispensed investigational product.

5.5. Administration

Investigational product will be dispensed to subjects to self-administer after appropriate training and specific instructions are provided. Instructions on dosing will be provided on the Subject Dosing Card. At all visits, the scheduled dose of investigational product will be taken by the subject in the clinic. At the end of each visit, sites will instruct subjects, when to take their investigational product prior to their next study visit. [REDACTED]

[REDACTED] Subjects should receive open-label investigational product at the Week 16 visit and should receive the first dose of the open-label investigational product at the clinic.

Tofacitinib tablets or matching placebo for oral administration may be taken with or without food. Subjects will swallow the investigational product whole, and will not manipulate or chew the investigational product prior to swallowing.

Subjects will be instructed to take their tablet investigational product twice daily (once in the morning and once in the evening approximately 12 hours apart) for a total of two tablets per day. Placebo tablets will match the 5 mg tablets in order to maintain the blind.

During the double-blind treatment period, if the investigator deems it necessary to withhold the investigational product to treat a non-serious infection or other medical condition, temporary withholding is permitted for up to 5 days. If temporary withholding of the investigational product exceeding 5 days is required for a medical reason (eg, elective surgery), the investigator must contact the Pfizer Medical Monitor for approval.

Temporary withholding of the investigational product, as described above, is permitted once during the study without obtaining prior approval from the Pfizer Medical Monitor. Any additional request(s) for temporary withholding of the investigational product during the double blind period require(s) documented approval by the Pfizer Medical Monitor.

Per Amendment 3, for subjects with suspected VTE, treatment with tofacitinib should be temporarily withheld while the subject is evaluated. If VTE is confirmed, discontinue treatment with tofacitinib (see Section 6.4: Subjects Discontinuation from the Investigational Product).

During the open-label period of the study, tofacitinib 5 mg BID may be temporarily discontinued for up to 28 consecutive days for laboratory abnormalities, for infections which do not meet criteria for serious infections (those requiring parenteral antimicrobial therapy or hospitalization), for surgical procedures or other moderately severe AEs. If treatment must be discontinued for more than 28 days, the subject should be withdrawn from the investigational product permanently (see [Section 6.4.2](#)).

5.6. Investigational Product Storage

The investigator or an approved representative, eg, pharmacist, will ensure that all investigational products are stored in a secured area with controlled access under required storage conditions and in accordance with applicable regulatory requirements.

Investigational products should be stored in their original containers and in accordance with the labels.

Any storage conditions stated in the Investigator's Brochure will be superseded by the storage conditions stated on the product label.

Site systems must be capable of measuring and documenting (for example, via a log), at a minimum, daily minimum and maximum temperatures for all site storage locations (as applicable, including frozen, refrigerated, and/or room-temperature products). This should be captured from the time of investigational product receipt throughout the study. Even for continuous-monitoring systems, a log or site procedure that ensures active evaluation for excursions should be available. The intent is to ensure that the minimum and maximum temperature is checked each business day to confirm that no excursion occurred since the last evaluation and to provide the site with the capability to store or view the minimum/maximum temperature for all non-working days upon return to normal operations. The operation of the temperature monitoring device and storage unit (for example, refrigerator), as applicable, should be regularly inspected to ensure they are maintained in working order.

Any excursions from the product label storage conditions should be reported to Pfizer upon discovery. The site should actively pursue options for returning the product to the storage conditions described in the labeling, as soon as possible. Deviations from the storage requirements, including any actions taken, must be documented and reported to Pfizer.

Once an excursion is identified, the investigational product must be quarantined and not used until Pfizer provides permission to use the investigational product. It will not be considered a protocol deviation if Pfizer approves the use of the investigational product after the temperature excursion. Use of the investigational product prior to Pfizer approval will be considered a protocol deviation. Specific details regarding information the site should report for each excursion will be provided to the site.

Site staff will instruct subjects on the proper storage requirements for take home investigational products.

5.7. Investigational Product Accountability

The investigator site must maintain adequate records documenting the receipt, use, loss, or other disposition of the investigational product supplies. All investigational products will be accounted for using a drug accountability form/record. All containers of the investigational product must be returned to the investigator by the subject at every visit and at the end of the trial.

5.7.1. Destruction of Investigational Product Supplies

The sponsor or designee will provide guidance on the destruction of unused investigational product (eg, at the site). If destruction is authorized to take place at the investigator site, the investigator must ensure that the materials are destroyed in compliance with applicable environmental regulations, institutional policy, and any special instructions provided by Pfizer, and all destruction must be adequately documented.

5.8. Concomitant Treatment(s)

It is important to be aware of, and document, **all** concomitant medications including: prescription, non-prescription (ie, over-the-counter) and herbal medications.

All local standard-of-care practices for the administration of permitted therapy (ie, background DMARD, contraceptives, rescue medication) including laboratory testing, follow-up care and contraindications should be performed according to local standards of care throughout the study. A subject who is receiving an allowed concomitant medication for any reason must be on a locally-approved medication and dose that is considered standard-of-care for the treated indication, and this must be documented in the case report form. It is recommended that subjects avoid changing non-prohibited prescription or non-prescription drugs, vitamins, and dietary supplements within 7 days or 5 half-lives (whichever is longer) prior to the first dose of investigational product and prior to study visits unless otherwise noted below, throughout the study.

Medications that are taken during the screening period (after informed consent is obtained and before the first dose of investigational product) will be documented as prior medications. Medications taken after the first dose of investigational product has been administered will be documented as concomitant medications. All concomitant medications taken during the study must be recorded in the study records with indication (as appropriate), daily dose and start and stop dates of administration. Subjects will be queried about concomitant medications at each study visit. Minimum guidelines for folate supplementation during study: Subjects on methotrexate must receive folate supplementation according to local methotrexate label guidelines and standard of care. A minimum of 5 mg weekly based on folic acid should be given unless local guidelines or standard of care state otherwise.

5.8.1. Biologic Medications

Prior treatment with bDMARDs including TNF inhibitors is permitted if they have been discontinued for at least five half-lives before randomization. See also [Section 4.1](#) for definition of a TNF inhibitor nonresponder. Subjects on bDMARDs including TNF inhibitors must be discontinued according to the following criteria:

- Etanercept (Enbrel®): Discontinued at least 4 weeks prior to the first dose of investigational product;
- Adalimumab (Humira®): Discontinued at least 10 weeks prior to the first dose of investigational product;
- Infliximab (Remicade®): Discontinued at least 8 weeks prior to the first dose of investigational product;
- Golimumab (Simponi®): Discontinued at least 10 weeks prior to the first dose of investigational product;
- Certolizumab (Cimzia®): Discontinued at least 10 weeks prior to the first dose of investigational product;
- Other bDMARDs: Discontinued at least 4 weeks or 5 half-lives (whichever is longer) washout period prior to first dose of study treatment after discussion with Sponsor.

5.8.2. Stable Background Pain or Other AS Therapy

Subjects taking permitted csDMARDs (eg, methotrexate (≤ 25 mg/week) or sulfasalazine (≤ 3 gm/day)), nonsteroidal anti-inflammatory drugs including selective cyclooxygenase-2 inhibitors (COX-2 inhibitors), and/or corticosteroids (≤ 10 mg prednisone mg/day) must remain on the same dose regimen throughout the study. Daily dosages of NSAIDs/COX-2 inhibitors, corticosteroids, opioids, and acetaminophen/paracetamol must be stable for 1 week prior to first study dose and must remain so during the study treatment period (Week 48) except if adjustment is needed to protect a subject's safety. Daily dosage of NSAIDs/COX-2 inhibitors, corticosteroids, opioids and acetaminophen/paracetamol must not be modified within the 24 hours prior to any study visit, except if adjustment is needed to protect a subject's safety.

Subjects using topical NSAIDs or anesthetics (ie, Ben-Gay®) on peripheral joints are allowed if stable for 1 week prior to the first study dose and must remain so during the study treatment period.

Glucosamine sulfate and chondroitin sulfate are allowed in the study but subjects should be on a stable dose for 1 week prior to first dose of investigational product and throughout the study.

The total daily dose of acetaminophen may not exceed 2.6 grams per day, and the total daily dose of opioid may not exceed the potency equivalent of 30 mg of orally-administered morphine (See [Appendix 5](#)).

5.8.3. Rescue Therapy

The only medications that are allowed for rescue are listed in [Appendix 6](#).

Increases of acetaminophen/paracetamol and opioids are allowable as rescue medication for no more than 10 consecutive days. Acetaminophen/paracetamol may be added or increased to a maximum of 2.6 gm/day. Combination products such as over-the-counter “cold remedies” or pain medications should be assessed for acetaminophen/paracetamol content so as the total dose will not exceed 2.6 gm/day. Opioids may be added or increased to a maximum potency equivalent of 30 mg of orally-administered morphine.

Subjects who require rescue for more than 10 consecutive days will be discontinued from the investigational product and be designated as discontinued from the investigational product for lack of efficacy. There is no limit to the duration of nonconsecutive use of rescue medications. In addition, subjects may not be dosed with rescue medication during the 24 hours prior to a study visit. In the judgement of the investigator, if rescue therapy has any effect on efficacy data collected during a study visit, this will constitute a protocol deviation. Baseline stable use of acetaminophen/paracetamol or opioids should NOT be discontinued in advance of study visits.

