6.4.2. Discontinuation Criteria (from the Investigational Product)

The investigational product will be discontinued in the event of any of the following:

- Serious infections, defined as any infection (viral, bacterial, and fungal) requiring parenteral antimicrobial therapy or hospitalization for treatment, or meeting other criteria that require the infection to be classified as a serious adverse event;
- Two sequential absolute neutrophil counts $<1.0 \times 10^9/L$ ($<1000/mm^3$);
- Two sequential absolute lymphocyte counts <500 lymphocytes/ mm^3 ;
- Two sequential hemoglobin values <8.0 g/dL (80 g/L) or decreases of $>30\%$ from baseline value;

- Two sequential platelet counts $<75 \times 10^9/L$ ($<75,000/mm^3$);
- Two sequential AST or ALT elevations ≥ 3 times the upper limit of normal with at least one total bilirubin value ≥ 2 times the upper limit of normal;¹
- Two sequential AST or ALT elevations ≥ 3 times the upper limit of normal accompanied by signs or symptoms consistent with hepatic injury (eg, new onset elevated PT/INR);¹
- Two sequential AST or ALT elevations >5 times the upper limit of normal, regardless of total bilirubin or accompanying signs or symptoms;¹
- Two sequential increases in serum creatinine $>50\%$ AND an absolute increase in serum creatinine >0.5 mg/dL ($44 \mu\text{mol/L}$) over the average of screening and baseline values;
- Two sequential creatine kinase (CK) elevations >10 times the upper limit of normal, unless the causality is known not to be medically serious (eg, exercise or trauma induced);
- A confirmed positive urine pregnancy test in a woman of childbearing potential;
- Any opportunistic infections considered significant by the investigator or the Sponsor;
- Requirement of rescue medication for more than 10 consecutive days;
- Subjects interrupting investigational product for more than 5 consecutive days during the double-blind portion or 28 consecutive days during the open-label treatment period or subjects who are less than 80% compliant with the dosage regimen for any two consecutive visit periods;
- Other serious or severe adverse events, in the opinion of the investigator or sponsor. Whenever possible, the investigator should consult with a member of the study team before discontinuation of the subject from the investigational product;
- If VTE is confirmed, discontinue treatment with tofacitinib.

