2.1. Study Objectives and Estimands

Primary Objective

1. To compare the efficacy of tofacitinib 5 mg BID versus placebo on the ASAS20 response rate at Week 16 in subjects with active AS that have had an inadequate response to previous treatment.

Key Secondary Objective

1. To compare the efficacy of tofacitinib 5 mg BID versus placebo on the ASAS40 response rate at Week 16 in subjects with active AS that have had an inadequate response to previous treatment.

Other Secondary Objectives

1. To compare the safety and tolerability of tofacitinib 5 mg BID versus placebo in subjects with active AS that have had an inadequate response to previous treatment.
2. To compare the efficacy (including health-related quality of life, function, pain, and fatigue) of tofacitinib 5 mg BID versus placebo at all time points in subjects with active AS that have had an inadequate response to previous treatment.

Tertiary/Exploratory Objectives

1. 
2. To evaluate the effect of tofacitinib 5 mg BID on lymphocyte subsets using FACS analysis.
3. To measure the effect of tofacitinib 5 mg BID on healthcare resource utilization at all collected time points.

2.1.1. Estimands for ASAS20 and ASAS40 at Week 16

Only discontinuation of the investigational product will be considered as an intercurrent event to define the estimands for this study. There are three estimands for the primary endpoint of ASAS20 at Week 16.

Estimand 1:

The first estimand of ASAS20 at Week 16 is a composite estimand that accounts for both treatment adherence and response. A responder is defined as having a response without discontinuation of the investigational product prior to Week 16. This is also called the Primary Estimand defined according to the primary objective. It includes the following four attributes:

- Population: Subjects who have active AS;
- Variable: ASAS20 response at Week 16. A subject after an intercurrent event of discontinuation of investigational product will be considered a non-responder for the visit of interest;
- Intercurrent event: The intercurrent event of discontinuation of the investigational product prior to Week 16 is captured through the definition of the composite variable. Data collected after discontinuation of the investigational product prior to Week 16 (ie, off-drug data) are not included to derive the response, ie, only On-Drug data are used (see [Section 9.1](#));

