4.2.3. Deviations Assessed Post-Randomization

These specific classes of protocol deviations will be assessed post randomization up to Week 16 only:

- Subjects who were randomized but took or received incorrect treatment other than the randomized treatment for the entire duration from Baseline through Week 16. This will be checked manually since there is no CRF page for this condition.
- Subjects who had <80% compliance on the investigational product's tablets on 2 consecutive visits (ie, 2 dosing periods) for the period from Baseline through Week 16. The investigational product compliance (%) will be derived from the total number of doses actually taken divided by the total number of doses expected to take per dosing period as recorded in Oral Dosing CRF page. Both the randomized treatments (ie, tofacitinib and placebo) will be taken into account.
- Subjects who were dosed with rescue medication for AS on the preceding day or the same day of the primary endpoint assessment at the Week 16 study visit. The rescue medication is recorded on the Concomitant Medications – Rescue Medications CRF page.

Each subject's presence on the list of exclusion from the PP analysis set means that there was at least one deviation for that subject.

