5.3. Methods to Manage Missing Data

As described in [Section 2.1.1](#), Estimands 1, 2 and 3 will be used for analyses of ASAS20 at Week 16. After accounting for the intercurrent event of discontinuation of investigational product ([Section 2.1.1](#)), missing ASAS20 values at Week 16 will be handled by setting the ASAS20 values to nonresponsive (in conjunction with Estimand 1 and Estimand 2). This method of handling missing response is known as missing response as non-response (MR=NR). Note that for Estimand 1 which employs the composite strategy ([Section 2.1.1](#)), this can be viewed as a composite endpoint in the sense that a response requires the subject

completes a visit of interest while receiving investigational product eg, Week 16, and achieves a response per the defined ASAS20 response criteria (otherwise it is considered a nonresponse). Note that when a subject has an ASAS20 assessment prior to or on the same date as the discontinuation of the investigational product within the Week 16 visit window, this ASAS20 assessment will be used to evaluate ASAS20 response as on-drug observation for Week 16 (this same rule will be applied to other visits and other applicable binary endpoints). For Estimand 3, missing response will not be explicitly imputed but will be implicitly handled in the GMMRM analysis. The above methods will also be applied to ASAS40 response at Week 16 as well as time points prior to Week 16 for both ASAS20 and ASAS40. The MR=NR in conjunction with Estimand 1 using on-drug data will be applied to all other response-type secondary endpoints (not Type I error controlled) including ASAS 5/6, ASAS partial remission, ASDAS_{CRP} clinically important improvement, ASDAS_{CRP} major improvement, ASDAS_{CRP} inactive disease, and BASDAI50 at all time points collected.

Repeated measures data for continuous and ordered-categorical (analyzed as continuous) endpoints will be analyzed with a MMRM model. This model will yield unbiased estimates and valid inferences in the presence of data that is MCAR or MAR (Rubin, 1987).² Hence missing values will not be explicitly imputed in the routine analysis using the repeated measures model. Continuous and ordered-categorical (analyzed as continuous) endpoints with only a single post-baseline visit will be analyzed with an ANCOVA model. Missing values will not be imputed when using the ANCOVA model.

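### A prolonged-rescue failure found only at the Week 16 visit can be scored as a primary response, because the SAP keys non-response to the recorded stop date

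*Protocol*

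**What the plan says.** **Protocol.** Section 5.8.3 states that subjects over the 10-day limit "will be discontinued from the investigational product and be designated as discontinued from the investigational product for lack of efficacy". Section 6.4.2 lists the same event as a mandatory stop: "Requirement of rescue medication for more than 10 consecutive days". Appendix 6 repeats it. Section 4.4 asks subjects to tell the site about any change in concomitant medication. At the Week 16 visit (6.2.6) the patient-reported outcomes come first, and concomitant treatments are reviewed later in the same visit.

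**SAP.** Section 2.1.1 says "Only discontinuation of the investigational product will be considered as an intercurrent event to define the estimands for this study". For Estimand 1, "A responder is defined as having a response without discontinuation of the investigational product prior to Week 16". Section 5.3 adds a timing rule for the case "when a subject has an ASAS20 assessment prior to or on the same date as the discontinuation of the investigational product". If that assessment lies in the window for Week 16, the consequence is stated as follows: "this ASAS20 assessment will be used to evaluate ASAS20 response as on-drug observation for Week 16". Section 9.1 agrees: the date on the End of Treatment disposition page divides the data, and visits on or before it are on-drug.

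Rescue enters the SAP's analysis sets only in 4.2.3, where rescue on the day before or the day of the Week 16 assessment removes a subject from the per-protocol set. That section also shows that the data exist: "The rescue medication is recorded on the Concomitant Medications" form, on its Rescue Medications page.

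**The concern.** The protocol treats a long rescue run as an efficacy failure in its own right. The SAP recognises it only through the product stop that should follow, and only by the date someone writes for that stop. Nothing in the SAP makes crossing the 10-day limit a non-response in itself.

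Two subjects with the same rescue history between Weeks 12 and 16 can therefore get opposite primary outcomes. One whose stop is dated before the Week 16 visit is a non-responder. One whose stop is dated on the visit day can be a responder. At stake is the coherence of the primary (ASAS20) and key secondary (ASAS40) composite: it could credit a response to a subject whom the protocol has just designated a lack-of-efficacy discontinuation.

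**Working it through.** **1. The plan's own figure.** Protocol 9.1 gives 120 per arm, 40% v 60%, two-sided 5%, about 89% power. With unpooled variance, as in the SAP's Z-test, SE = √(0.6×0.4/120 + 0.4×0.6/120) = √0.004 = 0.0632. Then 0.20/0.0632 = 3.162, and Φ(3.162 − 1.960) = 88.5%. Pooled null variance gives 87.7%. The stated power reproduces and is not in dispute.

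**2. Can the run fit?** SAP Table 5 sets the Week 12 and Week 16 targets at Days 85 and 113. The gap is 113 − 85 = 28 days. With the ±7-day visit windows it ranges from (113 − 7) − (85 + 7) = 14 to (113 + 7) − (85 − 7) = 42 days. A run of 11 days plus the rescue-free 24 hours before the visit needs 12 days, so it fits even in the shortest gap.

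**3. Can it surface after the endpoint data are collected?** Yes. All four ASAS20 domains come from the patient-reported outcomes (Protocol 7.2.1), which are done before the medication review.

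**4. How Estimand 1 scores each case**, for a subject who meets ASAS20 at Week 16:

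| Case | Recorded stop date | Week 16 data | Score |
|---|---|---|---|
| Run in Weeks 8–12, acted on at Week 12 | Week 12 | off-drug | non-responder |
| Run in Weeks 12–16, reported early | before the visit | off-drug | non-responder |
| Run in Weeks 12–16, found at Week 16, dated to a last dose the day before | before the visit | off-drug | non-responder |
| Run in Weeks 12–16, found at Week 16, dated to the decision | visit day | on-drug | **responder** |
| Limit crossed, product never stopped | none | on-drug | **responder** |

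The third and fourth rows differ only in a date convention. SAP 9.1 does not say whether the last dose or the decision to stop is the date that counts.

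**5. Do the supportive analyses catch it?** None does so specifically. The per-protocol criterion looks at two days only. Estimand 2, the GMMRM and both tipping point analyses use the observed response. Table 3 would list the subject as a responder, not under lack-of-efficacy discontinuations.

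**6. Size.** The documents give no rescue rates, so the counts below are assumptions. Start from the design rates, 72/120 v 48/120, and recode responders as non-responders. Use the unpooled Z and ignore strata. Each recoding moves an arm by 1/120 = 0.83 points.

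| Recoded, tofacitinib | Recoded, placebo | Difference (points) | p |
|---|---|---|---|
| 0 | 0 | 20.0 | 0.0016 |
| 1 | 0 | 19.2 | 0.0025 |
| 3 | 0 | 17.5 | 0.0059 |
| 5 | 0 | 15.8 | 0.0129 |
| 8 | 0 | 13.3 | 0.0367 |
| 9 | 0 | 12.5 | 0.0503 |
| 0 | 3 | 22.5 | 0.0003 |
| 0 | 5 | 24.2 | 0.0001 |
| 3 | 3 | 20.0 | 0.0015 |

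For nine on tofacitinib: 63/120 = 0.525; SE = √((0.525×0.475 + 0.4×0.6)/120) = 0.0639; Z = 0.125/0.0639 = 1.957.

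**The case against.** **The gap needs several things at once.** Protocol 4.4 asks for medication changes to be reported, and unplanned visits are allowed. If that works, the run is known and product is stopped before Week 16, and Estimand 1 already gives non-response. The stop must also be dated on the visit day. The scheduled clinic dose is held back, so at a morning visit the last dose would usually be the evening before. The subject must still meet ASAS20. All this stands, and it makes the case narrow.

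**The estimand is a stated choice.** Estimand 1 combines adherence and response. A subject stopped at Week 12 spends the last four weeks off drug; one stopped at the Week 16 visit has completed the blinded period. The same-day rule also applies at every visit. This stands in part: the two subjects are not identical in adherence. But the protocol attaches the failure label to the rescue run itself, not to time off drug.

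**Some handling exists.** Rescue is barred in the 24 hours before a visit, an effect of rescue on efficacy data is a protocol deviation, and SAP 4.2.1 lets deviations be added before unblinding. These can reach the per-protocol analysis but not the primary one. Nor does the 24-hour rule fully separate rescue from the endpoint, since the global and pain items ask about the last week (Protocol 7.2.9.3, 7.2.9.4). A run may equally have ended weeks earlier.

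**Stronger readings the documents do not support.** A reader might infer that the rule favours tofacitinib. No rescue rates by arm are given; if such subjects are mostly on placebo, the present rule is conservative. A reader might also infer that one subject could decide the trial. From 48 v 64 responders p = 0.037, and removing one tofacitinib responder gives p = 0.050. That is true of any binary endpoint at the boundary, and 48 v 64 is not the design assumption.

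**Conclusion.** The protocol and SAP are not aligned on this event. The protocol designates more than 10 consecutive rescue days a lack-of-efficacy discontinuation; the SAP makes it a non-response only if the recorded stop date precedes the Week 16 assessment. A responder score needs a run between Weeks 12 and 16 (or a criterion met earlier with no stop recorded), no action before the visit, a stop dated on the visit day or absent, and the ASAS criteria still met.

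The likely count is small but unknown, and so is the direction. The effect is 0.83 points per subject in the affected arm. At the design rates, losing significance would take nine recodings, all on tofacitinib; equal recoding in both arms leaves the difference at 20.0 points. The case rests on the coherence of the primary and key secondary endpoints, not on a demonstrated bias. It is worth correcting because the correction is cheap.

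**What to change.** In SAP 2.1.1, 5.3 and 9.1, state for Estimand 1 (ASAS20 and ASAS40): a subject whose Rescue Medications CRF page shows that the protocol's criterion of more than 10 consecutive days was met before the Week 16 assessment is treated as having had the discontinuation event on the day the criterion was met. That subject is a Week 16 non-responder whatever stop date is recorded. Amend the sentence in 2.1.1 that limits intercurrent events to product discontinuation so that it agrees. Keep the same-day on-drug rule for every other discontinuation.

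**Cost.** No new data are needed: the CRF page exists, and Protocol 5.8 already requires start and stop dates for concomitant medication. A few observed responders would be rescored, including any who met the criterion earlier but were never stopped; the SAP should say so openly. Protocol Section 9 requires major changes to the primary endpoint definition or its analysis to appear in a protocol amendment, so one may be needed. No rescue or stopping rule changes.
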